3.2. Study Definitions and Derived Variables

For calculations using the baseline value, the value obtained pre-first vaccination (Day 1) will be used. For samples with an AUC of zero at baseline, fold-rise will be calculated by dividing the post-vaccination result by the lowest reported value. AUC is calculated using the trapezoidal method applied to a serial dilution curve.

The Williams mean is a variation of the geometric mean using $\log(1+x)$ transformation of the data, where x is each data point. The Williams mean is used in cases where 0 is a possible and/or reported value of the data.

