6.4. Missing Data

There are no imputations planned for missing data.

For immunogenicity assays, any values below the lower limit of detection will be imputed as one-half the lower limit of detection for analysis purposes. Any such imputations will be noted in the corresponding analysis.

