Neutralization assays using SARS-CoV-2 pseudovirus neutralization assay (PsVNA) and focus reduction neutralization test (FRNT) will be run using serial dilutions against available variants (e.g., Beta, Delta, Omicron). ID₅₀ and ID₈₀ will be calculated using methodology such as a 5-parameter logistic regression model by the laboratory. ID₅₀ and ID₈₀ will be summarized by group using the geometric mean and 95% CI (using Student's t-distribution) at each post vaccination timepoint and overall peak GM (starting with Table 63 and ending with Table 182). Summaries of GMFR and seropositive are included starting with Table 239 and ending with Table 358. The ratio of the result for each variant divided by the result of the D614G variant will be calculated and summarized as the geometric mean ratio (GMR) (starting with Table 359 and ending with Table 382). Graphical displays for PsVNA and FRNT will include reverse

cumulative distribution plots (starting with [Figure 26](#), ending with [Figure 85](#); and starting with [Figure 110](#), ending with [Figure 169](#)), individual values over time (starting with [Figure 194](#), ending with [Figure 253](#); and starting with [Figure 278](#), ending with [Figure 337](#)), geometric mean over time (starting with [Figure 362](#), ending with [Figure 421](#); and starting with [Figure 446](#), ending with [Figure 505](#)) and distributions of responses over time (starting with [Figure 530](#), ending with [Figure 589](#); and starting with [Figure 614](#), ending with [Figure 673](#)).

Correlations between all assays will be displayed in a heatmap (starting with [Figure 674](#) and ending with [Figure 697](#)).

Summaries of N-antibody expression status and self-reported infection status will be reported in [Table 383](#), [Table 384](#), [Table 385](#), and [Table 386](#).

Individual immunogenicity responses are shown in [Listing 8](#).

Any additional variants of concern not listed in the appendices that are of scientific interest may be analyzed in an analogous manner in the final report.

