| Notes: N=Number of subjects in the mITT population. n=Number of subjects with results available at time point. GMFR=Geometric Mean Fold Rise, NE=Not Estimable. ^a Confidence interval calculated based on the Student's t-distribution ^b Exact binomial confidence interval calculated using the Clopper-Pearson methodology. | | | | |

Tables with Similar Format:

[Implementation notes: For tables using the PP population, update footnote to read: “Notes: N=Number of subjects in the Per Protocol population.”

For all AUC tables, add footnote reading: “AUC results reported as 0 were imputed to the lowest non-zero reported value for the purposes of fold-rise calculations.”]

- Table 192:** Serum IgG Binding Assay Arbitrary Units/mL Measured by ECLIA Geometric Mean Fold Rise and Seropositivity Results with 95% Confidence Intervals by Time Point and Treatment Group, S-2P-Wa-1 – Per Protocol Population, Treatment Arms 2A-B (Three Vaccinations)
- Table 193:** Serum IgG Binding Assay Arbitrary Units/mL Measured by ECLIA Geometric Mean Fold Rise and Seropositivity Results with 95% Confidence Intervals by Time Point and Treatment Group, RBD-Wa-1 – mITT Population, Treatment Arms 2A-B (Three Vaccinations)
- Table 194:** Serum IgG Binding Assay Arbitrary Units/mL Measured by ECLIA Geometric Mean Fold Rise and Seropositivity Results with 95% Confidence Intervals by Time Point and Treatment Group, RBD-Wa-1 – Per Protocol Population, Treatment Arms 2A-B (Three Vaccinations)
- Table 195:** Serum IgG Binding Assay Arbitrary Units/mL Measured by ECLIAv2 (4-plex) Geometric Mean Fold Rise and Seropositivity Results with 95% Confidence Intervals by Time Point and Treatment Group, S-2P-Wa-1 – mITT Population, Treatment Arms 2A-B (Three Vaccinations)
- Table 196:** Serum IgG Binding Assay Arbitrary Units/mL Measured by ECLIAv2 (4-plex) Geometric Mean Fold Rise and Seropositivity Results with 95% Confidence Intervals by Time Point and Treatment Group, S-2P-Wa-1 – Per Protocol Population, Treatment Arms 2A-B (Three Vaccinations)
- Table 197:** Serum IgG Binding Assay Arbitrary Units/mL Measured by ECLIAv2 (4-plex) Geometric Mean Fold Rise and Seropositivity Results with 95% Confidence Intervals by Time Point and Treatment Group, S-2P-B.1.351 – mITT Population, Treatment Arms 2A-B (Three Vaccinations)

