- Table 358: Focus Reduction Neutralization Test (TMPRS cells) ID₈₀ Geometric Mean Fold Rise and Seropositivity Results with 95% Confidence Intervals by Time Point and Treatment Group, B.1.1.529 – Per Protocol Population, Treatment Arms 2C-H (Two Vaccinations)**

Table 359: Pseudovirus Neutralization Assay ID₅₀ Geometric Mean Ratio to D614G Variant with 95% Confidence Intervals by Variant, Time Point, and Treatment Group – mITT Population, Treatment Arms 2A-B (Three Vaccinations)

| Variant | Planned Time Point | Statistic | Arm 2A (N=X) | Arm 2B (N=X) | All Subjects (N=X) |
|---------|--------------------|-----------|--------------|--------------|--------------------|
| B.1.351 | Day 1, Pre-Dose | n | | | |
| | | GMR | | | |
| | | 95% CI | | | |
| | Day 15 | n | | | |
| | | GMR | | | |
| | | 95% CI | | | |
| | Day 29 | n | | | |
| | | GMR | | | |
| | | 95% CI | | | |
| | Day 43 | n | | | |
| | | GMR | | | |
| | | 95% CI | | | |
| | Day 57 | n | | | |
| | | GMR | | | |
| | | 95% CI | | | |
| | Day 71 | n | | | |
| | | GMR | | | |
| | | 95% CI | | | |
| | Day 85 | n | | | |
| | | GMR | | | |
| | | 95% CI | | | |
| | Day 147 | n | | | |

| Variant | Planned Time Point | Statistic | Arm 2A (N=X) | Arm 2B (N=X) | All Subjects (N=X) |
|-----------|--------------------|-----------|-----------------|-----------------|-----------------------|
| | | GMR | | | |
| | | 95% CI | | | |
| | | n | | | |
| | Day 237 | GMR | | | |
| | | 95% CI | | | |
| | | n | | | |
| | Day 422 | GMR | | | |
| | | 95% CI | | | |
| | | n | | | |
| B.1.617.2 | Day 1, Pre-Dose | n | | | |
| | | GMR | | | |
| | | 95% CI | | | |
| | Day 15 | n | | | |
| | | GMR | | | |
| | | 95% CI | | | |
| | Day 29 | n | | | |
| | | GMR | | | |
| | | 95% CI | | | |
| | Day 43 | n | | | |
| | | GMR | | | |
| | | 95% CI | | | |
| | Day 57 | n | | | |
| | | GMR | | | |
| | | 95% CI | | | |
| | Day 71 | n | | | |

| Variant | Planned Time Point | Statistic | Arm 2A (N=X) | Arm 2B (N=X) | All Subjects (N=X) |
|---------|--------------------|-----------|-----------------|-----------------|-----------------------|
| | | GMR | | | |
| | | 95% CI | | | |
| | | n | | | |
| | Day 85 | GMR | | | |
| | | 95% CI | | | |
| | | n | | | |
| | Day 147 | GMR | | | |
| | | 95% CI | | | |
| | | n | | | |
| | Day 237 | GMR | | | |
| | | 95% CI | | | |
| | | n | | | |
| | Day 422 | GMR | | | |
| | | 95% CI | | | |
| | | n | | | |
| P.1 | Day 1, Pre- Dose | n | | | |
| | | GMR | | | |
| | | 95% CI | | | |
| | Day 15 | n | | | |

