| | | 95% CI | | | |
| | Day 237 | n | | | |
| | | GMR | | | |
| | | 95% CI | | | |
| | Day 422 | n | | | |
| | | GMR | | | |
| | | 95% CI | | | |

Notes: N=Number of subjects in the mITT population.
n=Number of subjects with results available at time point.
GMR=Geometric Mean Ratio, NE=Not Estimable.
Geometric Mean Ratio was calculated by taking the ratio of the result for each variant divided by the result of the D614G variant for each subject and calculating the geometric mean.
Confidence interval calculated based on the Student’s t-distribution

Tables with Similar Format:

Table 360: Pseudovirus Neutralization Assay ID₅₀ Geometric Mean Ratio to D614G Variant with 95% Confidence Intervals by Variant, Time Point, and Treatment Group – Per Protocol Population, Treatment Arms 2A-B (Three Vaccinations)

Table 361: Pseudovirus Neutralization Assay ID₈₀ Geometric Mean Ratio to D614G Variant with 95% Confidence Intervals by Variant, Time Point, and Treatment Group – mITT Population, Treatment Arms 2A-B (Three Vaccinations)

Table 362: Pseudovirus Neutralization Assay ID₈₀ Geometric Mean Ratio to D614G Variant with 95% Confidence Intervals by Variant, Time Point, and Treatment Group – Per Protocol Population, Treatment Arms 2A-B (Three Vaccinations)

Table 363: Pseudovirus Neutralization Assay ID₅₀ Geometric Mean Ratio to D614G Variant with 95% Confidence Intervals by Variant, Time Point, and Treatment Group – mITT Population, Treatment Arms 2C-H (Two Vaccinations)

| Variant | Planned Time Point | Statistic | Arm 2C (N=X) | Arm 2D (N=X) | Arm 2E (N=X) | Arm 2F (N=X) | Arm 2G (N=X) | Arm 2H (N=X) | All Subjects (N=X) |
|---------|--------------------|-----------|--------------|--------------|--------------|--------------|--------------|--------------|--------------------|
| B.1.351 | Day 1, Pre-Dose | n | | | | | | | |
| | | GMR | | | | | | | |
| | | 95% CI | | | | | | | |
| | Day 15 | n | | | | | | | |
| | | GMR | | | | | | | |
| | | 95% CI | | | | | | | |
| | Day 29 | n | | | | | | | |
| | | GMR | | | | | | | |
| | | 95% CI | | | | | | | |
| | Day 43 | n | | | | | | | |
| | | GMR | | | | | | | |
| | | 95% CI | | | | | | | |
| | Day 57 | n | | | | | | | |
| | | GMR | | | | | | | |
| | | 95% CI | | | | | | | |
| | Day 119 | n | | | | | | | |
| | | GMR | | | | | | | |
| | | 95% CI | | | | | | | |
| | Day 209 | n | | | | | | | |
| | | GMR | | | | | | | |
| | | 95% CI | | | | | | | |

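### The variant-to-D614G ratio (Tables 359-382) is built on half-LLOD values with no rule for undetectable pairs, so Day 1 ratios are artefacts and heavily censored cells mostly understate the loss

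*SAP*

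**What the plan says.** - Section 6.4: for immunogenicity assays, "any values below the lower limit of detection will be imputed as one-half the lower limit of detection for analysis purposes". It adds: "Any such imputations will be noted in the corresponding analysis".
- Section 8.2: the result for each variant "divided by the result of the D614G variant will be calculated and summarized as the geometric mean ratio (GMR"). The footnotes to the GMR shells make this a within-subject ratio, formed by "taking the ratio of the result for each variant divided by the result of the D614G variant for each subject", followed by a geometric mean with a Student's t interval.
- The GMR shells (Tables 359, 363, 367, 371, 375 and 379) print only n, GMR and 95% CI. Each variant block starts with a baseline row, for example "B.1.351 | Day 1, Pre-Dose | n". The footnotes define NE as not estimable but give no criterion for using it. None of them mentions values below the LLOD.
- Section 3.2, for 10-plex AUC values of zero at baseline: "fold-rise will be calculated by dividing the post-vaccination result by the lowest reported value". The implementation notes to both fold-rise shell sets (after Tables 191 and 215) say instead: "AUC results reported as 0 were imputed to the lowest non-zero reported value for the purposes of fold-rise calculations".

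**The concern.** A ratio of two substituted values carries no information about the ratio of the two titres, yet it enters the geometric mean and its interval like a measured one. Cohort 2 consists of people with no known infection, and a known positive serology is an exclusion. Most Day 1 pairs should therefore be undetectable for both viruses, and the Day 1 GMR would print as about 1 with a very narrow interval. A reader could take that as equal neutralisation.

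The same mechanism can act after the first dose, at late visits, for ID80, and for poorly neutralised variants. The distortion depends on the D614G titre. Two arms with the same true ratio but different titres would therefore show different GMRs, and Section 4.1 describes Cohort 2 as comparing strategies for cross-protective responses. The n in each cell counts available results, so the table does not show how many ratios are artefacts.

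**Working it through.** **No figure to reproduce.** The SAP gives no LLOD, SD, correlation or expected GMR for this analysis.

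**Inputs from the SAP.** Half-LLOD rule (6.4); per-subject ratio with t interval (8.2 and shells); 15 subjects in each of Arms 2A-B and 20 in each of Arms 2C-H (Table 1); a 6- to 9-fold loss against B.1.351 (Section 2).

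**Assumptions.** Log-normal paired titres, the same LLOD for both viruses, log10 SD 0.5 (also 0.3), correlation 0.7, n=20. D614G geometric means are expressed as multiples of the LLOD. The 30-fold loss is an assumed illustration.

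**Step 1: single pairs.**
- Both below LLOD: (LLOD/2)/(LLOD/2) = 1 for any true ratio. With unequal limits it is LLOD_variant/LLOD_D614G, an assay constant. If every pair in a cell is of this kind, all log ratios are identical, their SD is 0 and the t interval has zero width.
- Only the variant below LLOD: reported ratio ÷ true ratio = (LLOD/2)/(true variant titre). The loss is understated if the true titre is below LLOD/2 and overstated if it lies between LLOD/2 and LLOD.
- True loss 6-fold, D614G = 2×LLOD: the variant is 2/6 = 0.333×LLOD, replaced by 0.5. The ratio is 0.5/2 = 0.250 against 0.167, so the loss reads 4-fold.
- True loss 6-fold, D614G = 5×LLOD: the variant is 5/6 = 0.833×LLOD, replaced by 0.5. The ratio is 0.5/5 = 0.100, so the loss reads 10-fold.

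**Step 2: share censored (SD 0.5, true 8-fold loss).** P(variant < LLOD) = Φ(−log10(m/8)/0.5) and P(D614G < LLOD) = Φ(−log10(m)/0.5), with m the D614G geometric mean in LLOD units.
- m=2: Φ(1.204) = 89% and Φ(−0.602) = 27%.
- m=5: Φ(0.408) = 66% and Φ(−1.398) = 8%.
- m=10: Φ(−0.194) = 42% and Φ(−2) = 2%.

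**Step 3: the printed GMR.** 20,000 simulated samples per setting, n=20, SD 0.5, correlation 0.7:

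| True loss | D614G GM | Loss shown | 95% CI coverage |
|---|---|---|---|
| 8-fold | 2×LLOD | 3.5-fold | 6% |
| 8-fold | 5×LLOD | 6.0-fold | about 75% |
| 8-fold | 10×LLOD | 7.5-fold | 94% |
| 8-fold | 20×LLOD | about 8-fold | bias negligible |
| 30-fold | 5×LLOD | 9.2-fold | 0% |
| 30-fold | 10×LLOD | 15.9-fold | 24% |
| 30-fold | 20×LLOD | 23.4-fold | about 80% |

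With SD 0.3 and D614G at 10×LLOD, a true 8-fold loss shows as 8.7-fold, so the direction reverses slightly.

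**Step 4: a different pairing model** (SD 0.5, within-pair SD 0.2 log10). A true ratio of 0.167 (6-fold) is printed as 0.322 at 2×LLOD, 0.207 at 5×, 0.176 at 10× and 0.166 at 20×. At n=20 and 5×LLOD the t interval covers 79%. A left-censored bivariate-normal likelihood gives 0.168 there. The same fit for a 9-fold loss failed numerically, which bears on how much weight to put on it.

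**The case against.** **Other displays.** The strongest defence is that the GMR does not stand alone. Section 6.4 promises that imputations will be noted. Geometric means by variant are in Tables 63-182, post-vaccination seropositivity (above LLOD) is in Tables 239-358, and distribution plots and Listing 8 are planned. A careful reader can find which cells sit at the floor. This holds in part: those displays do not count pairs with one or both results undetectable, the seropositivity tables have no Day 1 row, and no GMR shell carries the promised note.

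**Importance.** The primary objective is safety. The secondary endpoint is response rate and magnitude, and no between-arm GMR contrast is specified. A reader might infer that the trial's main readout is compromised; the SAP does not support that.

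**Size.** The LLOD, SD, correlation and titre levels are all assumed. Section 4.2 reports strong responses after the second dose of mRNA-1273 in the earlier trial, and for the documented 6- to 9-fold loss the bias is small once D614G is well above the LLOD. This stands.

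**Direction.** A reader might infer that substitution always pulls the ratio toward 1. Steps 1 and 3 show that it does not.

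**AUC zeros.** A reader might infer from "fold-rise will be calculated by dividing the post-vaccination result by the lowest reported value" that the divisor can be 0. The notes to both fold-rise shell sets specify the lowest non-zero value, so no division by zero arises. Nor is the half-LLOD rule clearly a competing rule here, since the SAP states no LLOD for the 10-plex AUC. What remains is a mismatch in wording and scope: Section 3.2 addresses baseline zeros only, the notes all AUC zeros.

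**Conclusion.** The point stands in a limited form and is a cheap improvement worth making. It is certain from the text alone that a doubly undetectable pair yields a constant unrelated to the true ratio, that the Day 1 rows will consist largely of such pairs if the cohort is naive as intended, and that no rule or count covers them.

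Beyond Day 1 the size is conditional. Under SD 0.5, correlation 0.7, equal LLODs and n=20, a true 8-fold loss reads as about 3.5-fold at a D614G geometric mean of 2×LLOD and 6-fold at 5×LLOD, with intervals that undercover, and is nearly unbiased from 10×LLOD. A 30-fold loss is still visibly understated at 20×LLOD. At SD 0.3 a modest overstatement is possible. The document does not show which visits or variants will fall in these ranges, and the size at n=15 (Arms 2A-B) was not examined.

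**What to change.** 1. Remove the Day 1 rows from Tables 359-382.
2. In every remaining cell, print the number of pairs with the variant, D614G, or both below the LLOD.
3. Give the existing NE label a criterion: show NE where D614G is undetectable or most variant results are below the LLOD.
4. Add, as a sensitivity analysis only, a GMR from a left-censored paired likelihood on the log scale. It should not replace the simple ratio as main estimator: with 15 to 20 subjects it is least reliable in the most heavily censored cells.
5. As wording only, bring Section 3.2 into line with the shell notes on AUC zeros, in both the divisor (non-zero) and the scope (baseline or all zeros).

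Cost: SAP text and modest programming, fewer estimable cells, and reliance on log-normality in the sensitivity analysis.

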2.1. Purpose of the Analyses

These analyses will assess the immunogenicity and safety of mRNA-1273.351, given in vaccination schedules alone, sequentially, or co-administered with mRNA-1273 in naïve adults.

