4.4.5. Prior and Concomitant Therapy

Concomitant medications include only prescription medications and vaccines received outside of the study taken by the subject at the time of enrollment through 28 days after the last vaccination. At each study visit, if there are new SAEs, Protocol Specified AESIs, MAAEs, or NOCMCs, concomitant medications should be recorded on the appropriate DCF.

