6.2.2. Modified Intent-to Treat Population

The modified intent-to-treat (mITT) population includes all subjects who received at least one dose of the vaccine and contributed both pre- and at least one post-vaccination venous blood samples for immunogenicity testing for which valid results were reported.

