6.2.3. Per Protocol Population

In the final analysis, protocol deviations will be reviewed to determine which protocol deviations may affect the analysis. The per protocol (PP) population will then be defined – and this includes all subjects in the mITT subset with the following exclusions:

- Data from all available visits for subjects found to be ineligible at baseline.
- Data from all visits subsequent for the protocol deviations that are considered to affect the science.
- Data from any visit that occurs substantially out of window.

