8.2. Secondary Immunogenicity Analyses

Summaries and analysis of immunogenicity data will be presented for the mITT population. If there are protocol deviations which may affect the analysis, a per-protocol (PP) analysis may also be performed.

Seropositive is defined as above LLOD (if available).

Binding will be measured by three types of ECLIA assays. The first is a single-plex (ECLIA) that produces arbitrary units/mL that is a validated assay and can be converted to binding antibody units for Wa-1 S-2P binding. The second is a 4-plex (ECLIAv2) assay that is also validated and produces arbitrary units/mL to measure variant specific binding. The final assay is a 10-plex (ECLIAv2) that is a fit for purpose assay that produces area under the curve and is used to assess binding for variants of concern.

Seropositive rates, geometric mean fold rise (GMFR) and geometric mean (GM) or Williams mean of arbitrary units per mL (AU/mL), binding antibody unit/mL (BAU, only for Wa-1 [S2-P] variant), and AUC for SARS-CoV-2 will be calculated at Study Days 1 (GM only), 15, 29, 43, 57, 71, 85, 147, 237, and 422 (Arms 2A-B) and Days 1, 15, 29, 43, 57, 119, 209, 394 (Arms 2C-H) by treatment group and will include both tabular and graphical summaries. Seropositive rates, GMFR, and GM will be presented with their corresponding 95% confidence interval (CI) estimates (using Student's t-distribution for GM and GMFR and the Clopper-Pearson binomial method for seropositive) at each post vaccination timepoint and overall peak GM. Summaries of GM are included starting with Table 15 and ending with Table 62; and summaries of GMFR and seroconversion are included starting with Table 191 and ending with Table 238. Graphical displays will include reverse cumulative distribution plots (starting with Figure 2, ending with Figure 25; and starting with Figure 86, ending with Figure 109), individual values over time (starting with Figure 170, ending with Figure 193; and starting with Figure 254, ending with Figure 277), geometric mean over time (starting with Figure 338, ending with Figure 361; and starting with Figure 422, ending with Figure 445), and distribution of responses over time (starting with Figure 506, ending with Figure 529; and starting with Figure 590, ending with Figure 613).

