14.1.2 Demographic Data by Treatment Group

Table 12: Summary of Categorical Demographic and Baseline Characteristics by Treatment Group

| | | Arm 2A (N=X) | | Arm 2B (N=X) | | Arm 2C (N=X) | | Arm 2D (N=X) | | Arm 2E (N=X) | | Arm 2F (N=X) | | Arm 2G (N=X) | | Arm 2H (N=X) | | All Subjects (N=X) | |
|-----------------------------------|---|-----------------|---|-----------------|---|-----------------|---|-----------------|---|-----------------|---|-----------------|---|-----------------|---|-----------------|---|--------------------------|---|
| Demographic Category | Characteristic | n | % | n | % | n | % | n | % | n | % | n | % | n | % | n | % | n | % |
| Sex | Male | | | | | | | | | | | | | | | | | | |
| | Female | | | | | | | | | | | | | | | | | | |
| Ethnicity | Not Hispanic or Latino | | | | | | | | | | | | | | | | | | |
| | Hispanic or Latino | | | | | | | | | | | | | | | | | | |
| | Not Reported | | | | | | | | | | | | | | | | | | |
| | Unknown | | | | | | | | | | | | | | | | | | |
| Race | American Indian or Alaska Native | | | | | | | | | | | | | | | | | | |
| | Asian | | | | | | | | | | | | | | | | | | |
| | Native Hawaiian or other Pacific Islander | | | | | | | | | | | | | | | | | | |
| | Black | | | | | | | | | | | | | | | | | | |
| | White | | | | | | | | | | | | | | | | | | |
| | Multi Racial | | | | | | | | | | | | | | | | | | |
| | Unknown | | | | | | | | | | | | | | | | | | |
| Baseline N-antibody status | Negative | | | | | | | | | | | | | | | | | | |
| | Positive | | | | | | | | | | | | | | | | | | |

Table 13: Summary of Continuous Demographic and Baseline Characteristics by Treatment Group

| Variable | Statistic | Arm 2A (N=X) | Arm 2B (N=X) | Arm 2C (N=X) | Arm 2D (N=X) | Arm 2E (N=X) | Arm 2F (N=X) | Arm 2G (N=X) | Arm 2H (N=X) | All Subjects (N=X) |
|-------------------------------|--------------------|-----------------|-----------------|-----------------|-----------------|-----------------|-----------------|-----------------|-----------------|-----------------------|
| Age (Years) | Mean | | | | | | | | | |
| | Standard Deviation | | | | | | | | | |
| | Median | | | | | | | | | |
| | Minimum | | | | | | | | | |
| | Maximum | | | | | | | | | |
| Height (cm) | Mean | | | | | | | | | |
| | Standard Deviation | | | | | | | | | |
| | Median | | | | | | | | | |
| | Minimum | | | | | | | | | |
| | Maximum | | | | | | | | | |
| Weight (kg) | Mean | | | | | | | | | |
| | Standard Deviation | | | | | | | | | |

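### Section 8.2 collects N-antibody and infection data but uses them in no immunogenicity analysis, so the summaries for naïve adults have no prespecified infection-free counterpart

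*SAP*

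**What the plan says.** Section 2.1 states the purpose as assessing the variant vaccine "given in vaccination schedules alone, sequentially, or co-administered with mRNA-1273 in naïve adults". The secondary objective in Section 3.1 likewise refers to naïve individuals.

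- **Main set.** Section 8.2: "Summaries and analysis of immunogenicity data will be presented for the mITT population". Section 6.2.2 defines mITT as "all subjects who received at least one dose of the vaccine and contributed both pre- and at least one post-vaccination venous blood samples" with valid results. It has no condition on infection, N-antibody or outside vaccination.
- **PP set.** Section 8.2 says that if deviations may affect the analysis, "a per-protocol (PP) analysis may also be performed". Section 6.2.3 removes subjects found ineligible at baseline, visits substantially out of window, and "Data from all visits subsequent for the protocol deviations that are considered to affect the science". It does not list those deviations.
- **Eligibility (Section 4.3).** Exclusion 18 covers a history of COVID-19, a positive PCR test and, for Cohort 2, a serologic test already known to be positive. Exclusion 16 covers any other SARS-CoV-2 vaccine before or during the study.
- **Infection data.** Table 12 has a row for "Baseline N-antibody status", with negative and positive categories. Section 8.2: "Summaries of N-antibody expression status and self-reported infection status will be reported in" Tables 383 to 386. These give N-antibody positivity and self-reported infection at each serum visit, to Day 422 (Arms 2A-B) or Day 394 (Arms 2C-H), and at any time point. No other analytic use is stated.
- **Outside vaccines.** Section 4.4.5 counts as concomitant medication "vaccines received outside of the study taken by the subject at the time of enrollment through 28 days after the last vaccination".

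**The concern.** The plan measures the event that most disturbs its late immunogenicity summaries and then leaves it out of them. Serum is drawn up to 12 months after the last dose, and Section 8.2 plans Delta and Omicron neutralization assays. At those visits a GM over all mITT subjects mixes response to the study vaccine with response to infection or to another vaccine. The same holds for GMFR, seropositivity and the variant-to-D614G ratio (GMR).

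This affects how durability and breadth are read by arm. Infection occurs after randomisation. If it falls unevenly across arms of 15 or 20 subjects, differences between arms can reflect exposure as well as vaccine schedule. Without a prespecified rule, any infection-free summary would have to be defined after the data are known.

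**Working it through.** **Who stays in which set, as written**

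| Subject | mITT | PP |
|---|---|---|
| Day 1 N-antibody positive, not known before | stays | stays: only a known positive test makes the subject ineligible |
| Infected after enrolment | stays | stays: infection is not described as a deviation, and Tables 9 and 10 list no such exclusion reason |
| Outside SARS-CoV-2 vaccine during the study | stays | later visits may be dropped as a deviation under exclusion 16, but Section 6.2.3 does not say so and PP is optional |

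**Arm size.** The document gives no figure for this point. Its sample-size probabilities serve only to fix n, and they reproduce: 1 − 0.8^15 = 0.965 (stated as about 97%) and 1 − 0.8^20 = 0.988 (stated as about 99%).

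**Effect on a GM.** If k of n subjects have titres multiplied by f, the mean log titre shifts by (k/n)·log f, so the GM is multiplied by f^(k/n). The values of k and f are assumptions.

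| Affected | f = 2 | f = 4 | f = 10 | f = 20 |
|---|---|---|---|---|
| 1 of 20 | 1.04 | 1.07 | 1.12 | 1.16 |
| 4 of 20 | 1.15 | 1.32 | 1.58 | 1.82 |
| 6 of 20 | 1.23 | 1.52 | 2.00 | 2.46 |
| 1 of 15 | 1.05 | 1.10 | 1.17 | 1.22 |
| 3 of 15 | 1.15 | 1.32 | 1.58 | 1.82 |

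**Scale for comparison.** The planned t-based 95% CI of a GM extends by a factor of 10^(t·SD/√n) on each side. With n = 20, t = 2.093 and an assumed log10 SD of 0.4, this is 10^(2.093 × 0.4/4.472) = 1.54. For SD 0.3 to 0.5 the range is 1.38 to 1.71. One affected subject in 20 lies well inside that factor. Four in 20 with a 10-fold rise is about the same size as it.

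**Unequal arms.** If 10% are affected in one arm and 30% in another, the ratio of the two GMs is off by f^(0.30 − 0.10): 1.32 for f = 4 and 1.82 for f = 20.

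**GMFR.** A later infection raises only the post-vaccination value, so GMFR rises. A baseline positive raises the denominator as well. If the baseline is raised 10-fold and the post-vaccination titre 2-fold, the GMFR factor is (2/10)^(k/20): 0.92 for k = 1, 0.85 for k = 2 and 0.72 for k = 4.

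**The case against.** The case for leaving the plan alone has substance.

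- **A descriptive secondary endpoint.** Safety is primary, and Section 8 specifies no between-arm test or decision rule. The contamination is disclosed by arm and visit in Tables 383 to 386, and individual results are listed. This limits the severity, but disclosure does not tell a reader what the GM would be without the affected samples.
- **mITT regardless of infection is legitimate.** It describes everyone vaccinated. A reader might infer that a censored analysis should replace it as the main one. The documents do not support that. Censoring conditions on a post-randomisation event, and if low responders are infected more often it removes them and pushes late titres up.
- **PP can help with outside vaccines.** A reader might infer that such subjects contaminate every summary. Exclusion 16 together with the PP rule can remove their later visits, and PP tables are mocked up across the assays. What remains is that this is left to judgement.
- **Inflation is not shown.** A reader might infer that titres are inflated. No counts or titre rises are given, and GMFR can fall. Infection that affects arms equally would largely cancel in comparisons between them.
- **Peak GM is not defined.** A reader might infer that it records a post-infection value as the vaccine peak. The SAP does not say whether it is each subject's maximum or the highest visit GM. On the first reading, the post-infection value must also exceed that subject's own post-dose peak.
- **Late outside doses may be recorded.** Concomitant-medication collection stops at Day 85 or Day 57, but Tables 2 and 3 schedule interim history through the last visit. Whether a late dose would be captured cannot be settled from the SAP.

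**Conclusion.** The point holds as a gap in prespecification. No GM, GMFR, seropositivity, GMR or peak analysis uses N-antibody or infection status, although both are collected throughout and the question concerns naïve adults. Late GMs, and possibly peak GM, can be biased upward; GMFR can be biased in either direction.

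The size depends wholly on assumed counts and titre rises. It is minor for a single affected subject in an arm of 20. It becomes comparable with the GM's own confidence factor at about 4 of 20 with a 10-fold rise, given an assumed log10 SD near 0.4. A distorted comparison between arms further requires that the affected fraction or the titre rise differ by arm, which the SAP neither states nor rules out. The finding supports adding an analysis, not replacing mITT.

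**What to change.** 1. Keep all planned mITT tables on all data.
2. In Section 8.2, add a prespecified supplementary set of GM, GMFR, seropositivity, GMR and peak analyses. Restrict it to subjects who are N-antibody negative at Day 1. Remove each subject's results from the first N-antibody conversion, self-reported infection or recorded non-study COVID-19 vaccination onward.
3. In Section 6.2.3, name non-study COVID-19 vaccination as a deviation that affects the science, so that the PP handling does not rest on later judgement.

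The infection data are already planned, so the cost is SAP wording and a further run of existing table programs. The outside-vaccination rule can act only on doses that were recorded. The downsides are a smaller n at late visits and censoring that may be informative if low responders are infected more often. The two sets should therefore be presented and read together.
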